#### **1.1. Defining the Sample for Analysis**

For analysis of our primary adverse birth outcome, we will consider our primary sample to be mothers who experience either a fetal death or index birth (defined in section A.1 of the pre-analysis plan). For analysis of other outcomes, our primary sample will be mothers with an index birth, as many outcomes will not be observable in the case of fetal death.

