#### **A. Sample construction**

##### **A.1. Tracking study moms and babies**

All study outcomes will be measured using administrative data sources, which require matching to state administrative records. Because we plan to analyze outcomes for both the mother and child, we define several relevant samples for analysis of outcomes for the mother-child dyad. For most analyses, we will want to consider the sample of mother-baby dyads where a live birth occurred from the pregnancy in gestation at the time of enrollment. We call this the index birth. Mother-baby dyads who experience an index birth will be the primary sample for longitudinal analyses examining the impact of the program. As the mother is the unit of randomization and we expect multiple births to be rare, we plan to aggregate outcomes pertaining to children resulting from the index birth to the mother level. To identify the index birth, we first match the mother to a birth certificate in vital records. If the date of birth on the birth certificate is within 120 days before or after the estimated delivery date as reported on the baseline survey, we will consider the birth to be related to the pregnancy that was in gestation at the time of study enrollment. Births that occur outside of this window will not be included in the sample of index births.

We may also analyze outcomes for the broader sample of mothers with at least one matched administrative record related to the pregnancy reported at the time of enrollment. We will call this the index pregnancy. We define the index pregnancy as follows: when there is a matched index birth or fetal death in vital records, we define the pregnancy period as the period

---

 Specified in McConnell et al. (2020) as a death of the fetus occurring at or after 20 weeks of gestation.

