		
 
• A live birth certificate for the index birth,
 
• A Kuklina identified live birth in Medicaid claims or hospital discharge records occurring within 120 days of the expected delivery date
 
• A probable pregnancy loss in Medicaid claims or hospital discharge occurring during the index pregnancy
 
• A fetal death record in Vital Records occurring during the index pregnancy
 
• An antenatal care visit in Medicaid claims occurring during the index pregnancy
 
• Enrollment in Medicaid for pregnant women overlapping with the index pregnancy period
 

Index birth	Baseline survey, birth certificates	A birth identified by a matched birth certificate in Vital Records with a date of birth within 120 days before or after the estimated delivery date reported on the baseline survey.

Table 2. South Carolina Medicaid income eligibility criteria as a percent of the Federal Poverty Line over the study period

	Jan 2016	Jan 2017	Jan 2018	Jan 2019	Jan 2020	Jan 2021
Pregnant women 	199%	199%	199%	199%	199%	194%
Parents 	67%	67%	67%	67%	67%	95%
Children 0-1 	213%	213%	213%	213%	194%	208%
Children 1-5 	213%	213%	213%	213%	143%	208%
Children 6-18 	213%	213%	213%	213%	133%	208%

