##### **1.2.1 Primary Outcome**

Our primary outcome for this domain is an adverse birth outcome, which we define as having a preterm birth (less than 37 weeks' gestation), a newborn being small for gestational age (less than 10th percentile of US births conditional on gestational age), having low-birth weight (less than 2500 grams), or experiencing perinatal mortality (fetal death occurring at or after 20 weeks' gestation or mortality in the first 7 days of life). Data for the adverse birth outcome will come from South Carolina birth records, death records, and fetal death records.

For mothers with multiple births, we define the outcome based on having an adverse birth outcome for any child from the index pregnancy. While preterm birth and other adverse birth outcomes may be more common among multiple births, we anticipate that rates of multiple births will be equal across treatment and control arms. We may also explore alternative specifications of this outcome that include only singleton births.

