### 1.2.1 Secondary Outcomes

We will examine several secondary infant and maternal outcomes. For infant outcomes, we will examine each adverse birth outcome individually (SGA, preterm, low birth weight, perinatal mortality). We will also examine large-for-gestational age ( $>90^{\text{th}}$  percentile of US births conditional on gestational age), very low birth weight ( $<1500\text{g}$ ), a continuous measure of birth weight, and extremely preterm ( $<28$  weeks gestation) using birth certificate records. We will also examine neonatal morbidity, defined as assisted ventilation immediately after delivery, assisted ventilation for more than six hours, seizure, receipt of surfactant replacement therapy, or receipt of antibiotics for suspected sepsis using data from the birth certificate.ii,10,11 Finally, we will examine NICU admission of at least overnight, defined as a claim with a procedure code of 99468, 99469, 99477, 99478, 99479, or 99480 on the day of delivery and also on the following day.

We will also examine several maternal health related secondary outcomes at birth, including cesarean delivery (from the birth certificate) and severe acute maternal morbidity from hospital discharge and Medicaid data (as defined by the Centers for Disease Control and Prevention). We will examine maternal mortality up to one year after birth using vital records. We will examine receipt of any postpartum visit within the first 12 weeks postpartum using Medicaid claims data, defined as a claim with a diagnosis code of Z39 or a HCPCS code of 59430.

Next, we will examine the outcome of neonatal abstinence disorder and/or maternal drug/substance abuse both during the index pregnancy period and over the period spanning the index pregnancy and the first 24 months following the index birth. This outcome is defined as a composite outcome. While the outcome is only specified over the longer time-period in our protocol and trial registry, exploratory analysis of this outcome during the index pregnancy will be valuable because of the strong relationship between drug use and birth outcomes. We will define the composite outcome related to substance abuse as any record in the Medicaid claims or hospital discharge data with a code listed in Table 1.1. We will also examine robustness to a definition in which we exclude the tobacco codes which we expect to make up the majority of claims we observe matching to maternal substance use.

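### Read literally, SAP Addendum 1 section 1.1 analyses secondary perinatal mortality only in mothers with a live birth, which removes nearly all the fetal deaths its own definition includes

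*SAP*

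**What the plan says.** Addendum 1, section 1.1, sets two samples. The primary adverse birth outcome uses mothers with either a fetal death or an index birth. Everything else falls under a second rule, justified by what a fetal death leaves unrecorded: "For analysis of other outcomes, our primary sample will be mothers with an index birth, as many outcomes will not be observable".

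Section A.1 bases the index birth on dyads "where a live birth occurred from the pregnancy in gestation at the time of enrollment. We call this the index birth". Table 1 makes this operational as "A birth identified by a matched birth certificate in Vital Records with a date of birth within 120 days" of the estimated delivery date. Under index pregnancy, the same table has a separate entry: "A fetal death record in Vital Records occurring during the index pregnancy". The SAP therefore treats an index birth and a fetal death as different events with different records.

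The Primary Outcome section includes in the composite "experiencing perinatal mortality (fetal death occurring at or after 20" weeks, or death in the first 7 days of life. On sources it says: "Data for the adverse birth outcome will come from South Carolina birth records, death records, and fetal death records". The Secondary Outcomes section adds that "we will examine each adverse birth outcome individually (SGA, preterm, low birth weight, perinatal mortality").

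**The concern.** Perinatal mortality is a secondary outcome, so the second rule in 1.1 applies to it on a plain reading. That rule selects mothers with a live birth, while half of the outcome's definition is a pregnancy that ends without one. The reason given for the restriction is that many outcomes cannot be observed after a fetal death. That does not apply here: the fetal death is the event, and the SAP names the records that capture it.

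The purpose of analysing the components singly is to show which of them drives the composite. Under the literal rule, an effect of the programme on stillbirth would count in the composite and be absent from the one component meant to isolate it. The result would carry the name perinatal mortality without matching the SAP's definition, which would mislead anyone who compares or pools it. It would also condition on live birth, which is determined after randomisation.

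**Working it through.** **Definitions side by side.** The plan states no rate, sample size or power for perinatal mortality, so there is no figure to reproduce. The check is mainly a matter of combining definitions.

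1. Outcome: fetal death at or after 20 weeks, or death in the first 7 days (Primary Outcome; listed singly under Secondary Outcomes).
2. Sample for outcomes other than the primary composite: mothers with an index birth (1.1).
3. Index birth: a live birth found through a birth certificate (A.1, Table 1).
4. A singleton pregnancy that ends in fetal death meets 1 but not 3, so the mother is outside the sample.
5. The one exception is a multiple pregnancy with a stillborn and a live-born child, where the mother has an index birth. A.1 expects multiples to be rare.
6. Nothing else restores these mothers. Section 1.5 restates the wider sample, and adds its robustness check, for the adverse birth outcome, meaning the composite. The index-pregnancy sample in A.1, which would keep them, is optional: "We may also analyze outcomes for the broader sample of mothers with at least one matched administrative record".

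**Scale, under assumed rates.** Addendum 4, Table 3, gives 3,295 + 1,637 = 4,932 mothers with an index birth. Let f be the fetal death rate per pregnancy ending in fetal death or live birth, and e the 7-day death rate per live birth. Both are assumptions (f 0.4% to 1.0%, e 0.2% to 0.6%), for singletons only.

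- Fetal deaths = f × 4,932 / (1 − f)
- Early neonatal deaths = e × 4,932
- Share lost = fetal deaths / (fetal + early neonatal deaths)
- Rate as defined = f + e(1 − f); rate on live births = e

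| f / e | Fetal deaths | Pregnancies | Early neonatal deaths | Share lost | Rate as defined | Rate on live births |
|---|---|---|---|---|---|---|
| 0.4% / 0.2% | 19.8 | 4,952 | 9.9 | 19.8/29.7 = 67% | 0.60% | 0.2% |
| 0.7% / 0.4% | 34.8 | 4,967 | 19.7 | 34.8/54.5 = 64% | 1.10% | 0.4% |
| 1.0% / 0.6% | 49.8 | 4,982 | 29.6 | 49.8/79.4 = 63% | 1.59% | 0.6% |

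Pairing opposite extremes gives 19.8/49.4 = 40% (f 0.4%, e 0.6%) and 49.8/59.7 = 83% (f 1.0%, e 0.2%).

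**What an effect on stillbirth would look like.** Suppose the programme halved fetal deaths and averted cases had the same 7-day risk e as other live births. The home-visiting rate is f/2 + e(1 − f/2): 0.400%, 0.749% and 1.097%. Differences from usual care on the wider sample are −0.200, −0.349 and −0.497 points, with standard errors 0.220, 0.297 and 0.357 points (unpooled; arm size = live births / (1 − that arm's fetal death rate)). Two-sided 5% power is 0.149, 0.217 and 0.285. On live births the difference is e − e = 0 in all three cases.

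For a 30% relative reduction in the whole outcome, with f from 0.3% to 1.0% and e from 0.2% to 0.6%, power is about 13% to 30% on the wider sample and 8% to 15% on live births.

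**The case against.** The strongest reply is that the components were meant to keep the composite's sample. Section 1.1 sets a default and explains it by what cannot be observed in many outcomes, not all. The Secondary Outcomes section breaks up a composite already defined and calls each part an adverse birth outcome. Addendum 4, Table 5, marks perinatal mortality as both secondary and part of the primary. This reading is plausible and may be what was intended.

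It does not settle the matter. Section 1.1 ties the wider sample to the primary outcome, and perinatal mortality here is secondary. Addendum 3, section 3.1, names both fetal death and index birth when it wants that sample. Table 5 puts the same label on neonatal morbidity, which the Primary Outcome section does not include in the composite, so the label is weak evidence of a shared sample. The SAP also refers to a published protocol paper for its empirical approach. That paper is not among the documents and cannot be assumed to supply the rule.

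Two further objections stand. The size of the loss depends entirely on assumed rates. The zero effect on live births follows from the assumptions of the example: it illustrates the definition and is not evidence about the programme.

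**Conclusion.** As written, the sample rule and the outcome definition do not fit together, and section 1.1 needs correcting or, if inheritance was intended, confirming. The definitional conclusion needs no assumed numbers. The share of perinatal deaths lost, about 40% to 83%, and the 20 to 50 fetal deaths dropped do need them, as does any statement of how far the reported rate would fall below the defined one.

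A reader might infer more than this, and the documents do not support it:

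- **That the primary result is compromised.** Section 1.1 gives the composite the wider sample, so it is unaffected.
- **That the correction would reveal a significant effect.** Even with fetal deaths halved, power stays below 30% in each scenario. The gain is a correctly measured and labelled component.
- **That a published perinatal mortality result is wrong.** Addendum 4 says papers exist but not which sample they used for this outcome.
- **That the wider sample should be used everywhere the outcome appears.** In the Addendum 4 birth index, mothers with a fetal death would have no value on components such as NICU admission or neonatal morbidity, and no rule covers them.

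**What to change.** In section 1.1, add one sentence stating that perinatal mortality as a secondary outcome uses the same fetal-death-or-index-birth sample as the composite. If that was always the intent, the sentence confirms it. Leave the other outcomes as 1.1 has them.

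If a live-birth-only result has already been reported, label it early neonatal mortality and set the fuller-sample result beside it.

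For the Addendum 4 birth index, keep the sample on index births and label that component early neonatal mortality, unless a rule is first stated for mothers with a fetal death who lack values on the other components.

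The cost is small. The fetal death records are already a source for the composite, so the work is one sentence, at most one re-run, and a table footnote explaining why perinatal mortality has a slightly larger denominator than the other secondary birth outcomes. Widening the index would cost more, because the missing-component rule would have to be specified and justified.

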covering the weeks of gestation provided in the obstetric estimate on the vital record until the date of birth or fetal death. In the absence of an index birth or fetal death, we define the pregnancy period as the period covering 42 weeks prior to the expected delivery date provided on the baseline survey. We will consider a mother to be matched to the index pregnancy if she has any matched administrative records pertaining to the index pregnancy (including antenatal care, probable pregnancy loss or birth related records from Medicaid claims or hospital discharge or evidence of a birth or fetal death from vital records). Table 1 summarizes the definitions and data sources used to identify index pregnancies and live index births.

When tracking children in the study, we will define two key periods. We anticipate that the children of most mothers who enroll in the trial will be eligible for Medicaid for their entire first year of life, as the income requirements for infants are similar to those of pregnant women. However, as summarized in Table 2, in some years of the study, income requirements became more restrictive after the first year of the child's life. Furthermore, families whose children remain income-eligible into their child's second year of life must submit an annual review form to retain coverage. Therefore, we plan to measure outcomes for children resulting from index births in the study to two critical time points: through their first 12 months of life and through their first 24 months of life.

Table 1. Sample Tracking Definitions

Sample tracking measure	Data Source(s)	Definition
Index pregnancy	Birth Certificates, fetal death records, Medicaid claims and eligibility, hospital discharge	Having matched administrative records for one or more of the outcomes listed below during the period of the index pregnancy. This period is defined as covering the weeks of gestation provided in the obstetric estimate on the vital record until the date of birth or fetal death, when a mother has a matched index birth or fetal death record. In the absence of an index birth or fetal death, we define the pregnancy period as the time covering 42 weeks prior to the expected delivery date provided on the baseline survey.

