### **1.5. Endogeneity of Data Sources and Sensitivity Analysis**

Our primary analytic sample for the adverse birth outcome will focus on mothers with fetal deaths or index births observed in vital records, because these records contain more complete data on birth outcomes. In cases where a vital record exists, we will calculate the adverse birth outcome in the manner described in section 1.1. However, a small percentage of mothers who experience a fetal death or live index birth may have an error linking the mother's records to their child's vital records. To accommodate this possibility, we will perform a robustness check that utilizes the sample of mothers with a fetal death or index birth observed in either vital records, Medicaid claims or hospital discharge records.

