#### **1.5.1 Calculating Adverse Birth Outcomes Without Vital Records Data**

In this section, we define the calculation of the adverse birth outcome in instances where there is a matched record for the index birth or fetal death in hospital discharge record or Medicaid claims, but not in vital records.

We identify births in hospital discharge records and Medicaid claims using the ICD-10 diagnosis code definition of live birth in Kuklina et al. (2008) and listed in Table 1.8. We will use the ICD-10 diagnosis code Z3A to calculate gestational age. In cases where an ICD-10 code for gestational age is absent from the hospital or Medicaid claim record, we will calculate gestational age at birth using the admission date on the record and the expected due date as given in the baseline survey. The preterm birth component of the adverse birth outcome will be coded as 1 if the gestational age on the health record is less than 37 weeks, or, if the record contains a diagnosis code P07.30-P07.39. The low-birth weight component will be coded as 1 if the record contains a diagnosis code P07.0-P07.18. The SGA component will be coded as 1 if the record contains a diagnosis code of P051. Fetal deaths will be identified with the codes in Table 1.9 when accompanied by an ICD-10 diagnosis code Z3A for gestational age of at least 20 weeks.

---

Table 1.8. Codes to Identify Live Births

ICD-10 Code(s)	Code Description	Exclusion Code
080, 082	Encounter for delivery	No
Z37	Outcome of delivery	No
10D00Z0, 10D00Z1, 10D00Z2	Extraction of products of conception	No
10D07Z3, 10D07Z4, 10D07Z5, 10D07Z6, 10D07Z7, 10D07Z8	Forceps/Vacuum/Breach	No
OW8NXZZ	Episiotomy	No
10A07ZZ, 10A00ZZ, 10A03ZZ, 10A04ZZ, 10A07ZX, 10A07ZW, 10A07Z6, 10A08ZZ	Abortion of products of conception	Yes
0019	Hydatidiform mole, unspecified	Yes
0048	Shock following (induced) termination of pregnancy	Yes
002	Missed abortion	Yes
000	Tubal pregnancy without intrauterine pregnancy	Yes
003	complete or unspecified spontaneous abortion without complication	Yes
008	Complications following ectopic and molar pregnancy	Yes

Table 1.9. Fetal Death Codes

ICD-10 Code(s)	Code Description	Exclusion Code
Z37.1	Single stillbirth	No
Z37.4	Twins, both stillborn	No
Z37.7	Other multiple births, all stillborn	No
P95	Stillbirth on child claims (occasionally appears on Mother claims)	No
036.4	Maternal care for intrauterine death	No

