### **3.4. Attrition and Missing Outcome Data**

As described in section 1.4 some mother-babies will be matched to a childbirth-related Medicaid claim or discharge record but unmatched to a birth certificate record or fetal death vital record. We will conduct a sensitivity analysis that will include these study participants, in addition to the main sample following procedures defined in section 1.6.1. For mother-babies without a birth certificate or fetal death record, we will use hospital discharge data as the date of birth or fetal death.

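### The only committed analysis of severe maternal morbidity and one-year maternal mortality leaves out mothers with a fetal death, although both outcomes can be read from the mother's own records; the numerical effect is small

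*SAP*

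**What the plan says.** SAP Addendum 1, section 1.1 uses mothers with a fetal death or an index birth for the adverse birth composite. For all other outcomes, "our primary sample will be mothers with an index birth, as many outcomes will not be observable in the case of fetal death". Section A.1 defines an index birth as a live birth, matched to a birth certificate within 120 days of the due date.

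The Secondary Outcomes part of section 1.2 lists two serious outcomes of the mother. One is "severe acute maternal morbidity from hospital discharge and Medicaid data". The other reads: "We will examine maternal mortality up to one year after birth using vital records".

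The SAP also says how a fetal death is found and dated:
- Section A.1 uses the vital record, with the pregnancy period "covering the weeks of gestation provided in the obstetric estimate on the vital record until the date of birth or fetal death".
- Section 1.5.1 covers cases without a vital record: "Fetal deaths will be identified with the codes in Table 1.9", given a gestational-age code of at least 20 weeks. Table 1.9 includes a code for the mother, "Maternal care for intrauterine death".
- Section 3.4 of Addendum 3 says of women with neither vital record: "we will use hospital discharge data as the date of birth or fetal death".

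Section 3.1 of Addendum 3 takes women with a fetal death or index birth as its sample for birth spacing and contraception.

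**The concern.** Section 1.1 justifies the restriction by what cannot be observed after a fetal death. A stillborn child has no neonatal course to record, so the reason holds for outcomes such as NICU admission. It does not hold for a complication of the mother's own delivery or for her death in the following year.

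Two things are at stake. First, mothers whose pregnancy ended in fetal death are absent from the main report of the two most serious maternal outcomes, although the data sources are already in use. Second, live birth occurs after randomisation, and fetal death is a component of the primary composite (section 1.2.1), so the plan itself allows that the programme may change it. Restricting to live births where the data do not require it is avoidable conditioning on a post-randomisation event.

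**Working it through.** **Step 1. Does any other section commit a wider sample for these two outcomes?**

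| SAP section | What it provides | Closes the gap? |
|---|---|---|
| A.1 | Outcomes may also be analysed among mothers with any record of the index pregnancy | No: optional, names no outcome |
| 1.4 | Counts of pregnancy loss, linking errors and unmatched pregnancies by arm | No: counts pregnancy outcomes, not maternal events |
| 1.5 | A robustness check in "the sample of mothers with a fetal death or index birth observed in either vital records, Medicaid claims or hospital discharge records" | No: written for the adverse birth outcome |
| 3.1 | Fetal death or index birth | No: Addendum 3 outcomes only, but shows the sample is feasible |

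The index-birth analysis is therefore the primary one and the only one committed to.

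**Step 2. How many mothers are left out?** The plan gives no figure on this point to reproduce. Addendum 4, Table 3 gives 3,295 + 1,637 = 4,932 mothers with an index birth. Let f be the share of fetal deaths among pregnancies ending in fetal death or index birth (assumed 0.5% to 1.5%). Mothers left out = 4,932 × f/(1 − f):
- f = 0.5%: 24.8
- f = 1.5%: 75.1, of whom 3,295 × 0.015/0.985 = 50.2 are in the NFP arm

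**Step 3. Morbidity events left out.** Assume 1.75% after an index birth: 4,932 × 0.0175 = 86.3 events (57.66 NFP, 28.65 control). Assume 5% to 10% after a fetal death, with 15% as an extreme:
- low: 24.8 × 5% = 1.24; 1.24/87.55 = 1.4% of all events
- high: 75.1 × 10% = 7.51; 7.51/93.82 = 8.0%
- extreme: 75.1 × 15% = 11.27; 11.27/97.58 = 11.5%

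**Step 4. Effect on the arm contrast.** Two scenarios, each with SE = √[p(1 − p)(1/3,295 + 1/1,637)].

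- *Mothers moved into the NFP live-birth sample.* Suppose NFP prevents 30% of fetal deaths at f = 1.5%, and these mothers keep the higher morbidity risk. Then 0.3 × 50.2 = 15.05 mothers enter. At 10% risk the NFP rate becomes (57.66 + 1.505)/(3,295 + 15.05), a rise of 0.0375 percentage points; at 15% risk the rise is 0.0603 points. With p = 1.75% the SE is 0.3965 points, so the shifts are 0.09 and 0.15 SE.
- *Index-birth contrast against the wider sample.* Suppose fetal death falls from 1% to 0.5%, with morbidity 2% after live birth and 20% after fetal death in both arms. The index-birth difference is 0. In the wider sample the control rate is 0.02 × 0.99 + 0.20 × 0.01 = 2.18% and the NFP rate is 0.02 × 0.995 + 0.20 × 0.005 = 2.09%, a difference of −0.09 points. With p = 2% the SE is 0.423 points, so the shift is 0.21 SE.

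Neither scenario is an upper bound.

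**Step 5. Deaths left out.** Assume 20 to 800 deaths per 100,000 in the year after a fetal death: 24.8 × 0.0002 = 0.005 to 75.1 × 0.008 = 0.60. For comparison, an assumed 0.05% one-year mortality in 4,932 mothers gives about 2.5 deaths.

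**The case against.** A reader might infer that these outcomes will be analysed only in live births. The documents do not support that. Section 1.1 names a primary sample, and section A.1 leaves a broader one open. Perinatal mortality, listed separately among the secondary outcomes, includes fetal death by definition, so section 1.1 must be a default rather than an exclusive rule. This stands, and it is why the point concerns what is committed. It does not supply the missing exception for the two maternal outcomes.

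A common sample for secondary outcomes is also a defensible convention, and the SAP says that many outcomes are unobservable, not all. Morbidity is listed with outcomes at birth, and Addendum 4, Table 5 places it in an index beside NICU admission and neonatal morbidity. Convenience of reporting is a fair reason, but it is not the reason given.

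The mortality definition shares the cause: it counts from birth, so changing the sample alone is not enough. This stands and is carried into the fix.

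The SAP also defers its empirical approach to a published protocol paper, and its morbidity definition to an outside agency. Neither was available, so a sample rule stated there cannot be excluded.

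Finally, no material consequence is shown. That is correct for inference; every rate used above is assumed.

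**Conclusion.** The point holds as a minor one. The stated reason for the live-birth restriction does not apply to severe acute maternal morbidity or one-year maternal mortality, and nothing in the supplied documents commits to a sample that includes mothers with a fetal death.

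The size is small, on assumed rates throughout. About 25 to 75 mothers are left out, with about 1 to 8 morbidity events (about 11 at the 15% extreme). The treatment contrast moves by roughly 0.1 to 0.2 SE. For mortality, fewer than one omitted death is expected, although with so few deaths overall a single one would be a large relative change.

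A reader might infer that the maternal results are biased enough to mislead. The documents give no fetal-death, morbidity or mortality rates that would support this, and the scenarios tried come nowhere near it. What is gained is completeness of serious maternal events by arm.

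**What to change.** In section 1.1, add one exception: analyse severe acute maternal morbidity and maternal mortality in mothers with a fetal death or index birth, the sample already used for the composite and in section 3.1. Take morbidity at that delivery. Count mortality to one year from the date of birth or fetal death, and amend the mortality definition under Secondary Outcomes to match. Date the event from the vital record or, where there is none, from hospital discharge data as in section 3.4. That section does not name the date field; the admission date, which section 1.5.1 uses to calculate gestational age, would serve. Keep the index-birth version as a sensitivity analysis.

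Addendum 4 describes the trial manuscripts as published or forthcoming. For any already published, give supplementary counts by arm, labelled post hoc.

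The cost is low, because the sample and data sources are already in the plan. There are two downsides. These outcomes would use a different sample from the other secondary outcomes and from the Addendum 4 birth index. The new sample also still conditions on a live birth or on reaching 20 weeks, so the conditioning is reduced but not removed.
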